Participants: Up to 25 adult patients who are at least 18 years of age with hemicrania continua will be enrolled into the screening phase of this study at Mayo Clinic Arizona. Enrollment will stop once 25 subjects provide headache diary during the screening phase that meets eligibility criteria (i.e. meet diagnostic criteria for hemicrania continua). Exclusion and inclusion criteria will be modeled after those used in the phase 2 and 3 trials of erenumab for the prevention of migraine and adapted for the diagnosis of hemicrania continua.^{10,11} Potential participants will be excluded if they have active chronic pain conditions other than hemicrania continua (e.g. chronic pelvic pain) or acute pain conditions (e.g. recent surgery).

Subject Eligibility

Inclusion Criteria

- Adults ages 18 and over
- At least a 12 month history of hemicrania continua according to International Classification of Headache Disorders, 3rd Edition (ICHD-3)¹
- Previous or current complete response to indomethacin
- Stable preventive treatment for at least 2 months and no anticipated need to adjust/add current headache prevention treatment

Exclusion Criteria

- Nonresponse to a therapeutic dose of indomethacin for hemicrania continua when used for at least 1 week
- Pregnant or lactating subjects
- Use of barbiturate or opioid >6 days per month; history of chronic migraine
- History of previous trigeminal-autonomic cephalgia

- History within previous 2 months of interventional procedure for headache (occipital or other extracranial nerve block, sphenopalatine ganglion block, cervical facet block, facet rhizotomy)
- History of cranial nerve/rhizolysis
- Botulinumtoxin injection within previous 4 months
- Parenteral infusion of an oral corticosteroid use for more than 3 days within 4 weeks prior to screening phase

Screening Phase (1 week) (Day -7)

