At this initial visit, participants will be screened for inclusion/exclusion and data on their demographics, headache characteristics, current and past treatments, and medical history will be collected. Those meeting criteria for further participation will have measurement of vital signs and urine pregnancy testing (for women of childbearing potential), and will be trained on how to use the headache diary. Patients will be instructed to keep a prospective headache diary for the next week. We assume that up to 20% of individuals participating in the screening phase will not meet the inclusion criteria and/or diary compliance minimum and thus will not continue in this study. It is anticipated that 25 patients will be enrolled in the screening phase of the study to obtain 20 evaluable patients. If a subject is on indomethacin for the prevention of hemicrania continua, indomethacin will be stopped at this visit.

Baseline (treatment) Visit (Day 0)

Patients will return for a baseline visit after 1 week (i.e. 7 days since start of screening phase) of prospective headache diary collection. Diary compliance and eligibility for study inclusion will be assessed. Patients who still meet eligibility criteria will have measurement of vital signs and urine pregnancy testing will be conducted for women of childbearing potential. Levels of depression and anxiety will be measured using the Beck Depression Inventory and State-Trait Anxiety Inventory, respectively. Functional disability will be assessed with the Migraine Disability Assessment (MIDAS).

Treatment with Erenumab (Day 0)

Patients will receive treatment with 140 mg of erenumab via subcutaneous injection during their baseline visit. Patients will either be taught how to self-inject by a qualified research team member and then will do so under research team observation or receive the injections administered by a qualified research team member. Injections will be administered in the abdomen (except for a two inch area right around the navel), thigh, or outer area of upper arm (if someone else is injecting the patient) according to patient preference and will consist of two consecutive 70 mg injections. The second injection will not be given in the same spot as the first injection.

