According to the FDA label for erenumab, it is contraindicated in patients with serious hypersensitivity to erenumab-aoe or to any of the excipients. Reactions have included anaphylaxis and angioedema.

Erenumab has been shown to be well tolerated and associated with few side effects. The most common side effects are injection site pain, erythema, and edema. Less than 5% of patients in the phase II and III clinical trials reported these side effects. In addition, constipation was reported by approximately 3% of individuals receiving erenumab.

Hypersensitivity Reactions: If a serious hypersensitivity reaction occurs, discontinue administration of AIMOVIG and initiate appropriate therapy. Hypersensitivity reactions can occur within hours to more than one week after administration.

Hypertension: Development of hypertension and worsening of pre-existing hypertension have been reported following the use of AIMOVIG in the postmarketing setting. Many of the patients had pre-existing hypertension or risk factors for hypertension. Hypertension may occur at any time during treatment but was most frequently reported within seven days of dose administration.

Constipation with Serious Complications: Serious complications of constipation may occur.

Potential risks associated with erenumab use during pregnancy and lactation are not established.

Protected health information (PHI) is being collected. Although measures are taken to reduce the risk, it is possible that there could be inappropriate access to the PHI by individuals not approved for such access.

Protection Against Risks:

Individuals who are known to be pregnant or lactating will be excluded from study participation.

Women of childbearing potential who are not known to be pregnant will have urine pregnancy testing before the 4 week run-in phase and prior to each of the two erenumab treatments. Women found to be pregnant will not receive any additional treatments with erenumab. Women of childbearing potential will be required to use a reliable form of contraception from the start of the run-in phase through 16 weeks after the last dose of erenumab (details provided in 'eligibility criteria' section of this protocol).

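### The protocol states a hypersensitivity contraindication to erenumab that its eligibility criteria and its risk-protection measures do not carry

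*Combined protocol and SAP*

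**What the plan says.** Possible Risks, relying on the FDA label, says of erenumab that "it is contraindicated in patients with serious hypersensitivity to erenumab-aoe or to any of the excipients. Reactions have included anaphylaxis and angioedema". The same section adds that such reactions may appear from hours to more than a week after dosing. If a serious one occurs, administration is to stop and suitable treatment is to begin.

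The Participants paragraph describes where the criteria come from: "Exclusion and inclusion criteria will be modeled after those used in the phase 2 and 3 trials of erenumab for the prevention of migraine", adapted to hemicrania continua. It adds one exclusion in prose: "Potential participants will be excluded if they have active chronic pain conditions other than hemicrania continua", or an acute pain condition. The bulleted exclusions then run from "Nonresponse to a therapeutic dose of indomethacin for hemicrania continua when used for at least 1 week" to "Parenteral infusion of an oral corticosteroid use for more than 3 days within 4 weeks prior to screening phase".

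For Day 0, the Baseline (treatment) Visit section says: "Diary compliance and eligibility for study inclusion will be assessed". It continues: "Patients who still meet eligibility criteria will have measurement of vital signs and urine pregnancy testing will be conducted for women of childbearing potential". The next section gives the treatment: "Patients will receive treatment with 140 mg of erenumab via subcutaneous injection during their baseline visit", as two 70 mg injections one after the other.

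**The concern.** A contraindication takes effect in a trial through selection before dosing, and here the risk section and the selection criteria do not match. The eligibility check can apply only the criteria that exist. A site that followed the list exactly would find a patient with a past serious reaction to the drug or an excipient eligible.

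The single-visit design makes this matter more. In a repeated-dose trial, an instruction to stop after a reaction protects against the next dose. Here there is no later dose, so the instruction to stop can at most prevent the second of the two injections. The protocol's own time course, hours to more than a week, makes even that unlikely. Safety and tolerability is also one of the two Specific Aims, so the dosed population should agree with what the protocol says about who may be dosed.

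**Working it through.** The plan gives no figure on this point and no arithmetic applies. The check compares the stated contraindication with every place where the protocol could act on it before dosing.

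1. **Inclusion criteria (4 bullets).** They cover age, at least 12 months of hemicrania continua, response to indomethacin, and stable preventive treatment. Bullets on hypersensitivity: 0 of 4.
2. **Exclusion criteria (8 bullets).** In order: indomethacin nonresponse; pregnancy or lactation; barbiturate or opioid use together with chronic migraine; previous trigeminal-autonomic cephalgia; recent interventional headache procedures; cranial nerve procedure or rhizolysis; botulinum toxin; corticosteroids. Bullets on hypersensitivity, allergy, excipients or previous erenumab: 0 of 8. Previous exposure to erenumab is not excluded, so a past reaction to it is not ruled out indirectly.
3. **Prose exclusion under Participants.** It concerns other chronic or acute pain only.
4. **Modelling on the phase 2 and 3 erenumab trials.** The criteria are modelled on those trials and adapted. They are not adopted by reference, and the trials' criteria are not reproduced. The adapted list is written out without this item.
5. **Screening Phase.** Medical history and current and past treatments are recorded, so a past reaction could come to light. No rule says what follows if it does.
6. **Day 0.** Four things are checked: diary compliance, eligibility, vital signs and, for women of childbearing potential, a urine pregnancy test. The eligibility check inherits the gap in items 1 to 3, and the other three checks do not bear on hypersensitivity.
7. **Protection Against Risks.** It covers pregnancy, lactation, contraception and data privacy, with nothing on hypersensitivity.
8. **Hypersensitivity instruction under Possible Risks.** It applies only once a reaction has occurred.

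No item turns the stated contraindication into a pre-dose criterion.

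Two further comparisons suggest a drafting mismatch and not a deliberate choice. First, Protection Against Risks refers to a 4-week run-in, two erenumab treatments and contraception details in the eligibility section. The design has a 1-week screening phase and one dose, and Subject Eligibility contains no contraception details. Second, the Schedule of Events marks eligibility at screening only, whereas the Baseline (treatment) Visit section has it assessed on Day 0 as well. The second mismatch is separate and minor. It affects every criterion equally, and a history of serious hypersensitivity is unlikely to arise in seven days without the drug.

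**The case against.** The best reply is that the bullet list is not the whole protocol. The contraindication stands in the same document, and the investigator takes a medical and treatment history. Case report forms are listed for prior headache medications and personal medical history. The Informed Consent section makes participant safety a primary concern, and each injection is given or watched by the research team. On this view the documents are silent in one list and do not contradict themselves. In addition, the Inclusion and Exclusion Criteria form is listed but not reproduced, so it may already carry the item.

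Much of this stands. It makes dosing such a patient improbable, and it limits what can be said about practice. It does not supply the missing criterion: history is collected but tied to no rule, and the safeguard depends on the investigator carrying a statement from one section to another.

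Four stronger readings are tempting, and the documents do not support them.

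- A reader might infer that these are the only patients the protocol bars from the drug and then admits. Pregnant and lactating people are also barred, and for them the criteria and the pregnancy tests do the work.
- A reader might infer that eligibility and diary compliance are the only checks before dosing. Vital signs and pregnancy testing are also required on Day 0.
- A reader might infer that a foreseeable reaction would pass as a routine safety result. Definition of Serious Adverse Events names a hypersensitivity reaction as an example that could be classed as serious. Relatedness must be assessed, and Adverse Events Analysis reports nature, severity and relationship.
- A reader might put a size on it as one event among about 20 dosed patients. That proportion is the same for any event and says nothing about how likely this one is.

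**Conclusion.** The gap is real and limited. The protocol states a contraindication that 0 of 4 inclusion bullets, 0 of 8 exclusion bullets, the prose exclusion and the risk-protection section reflect. The written criteria therefore do not screen out a contraindicated patient before a dose that is completed at one visit. It should be corrected, because following the eligibility rules to the letter gives a worse safety outcome than the protocol's own risk statement intends, and correcting it costs very little.

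The conclusion rests on the eligibility section being complete as it appears, and on modelled after not meaning adopted in full. The number of patients affected is not in the documents; that it is small is an assumption. The documents do not support the inference that such a patient would in fact be dosed.

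**What to change.** Reconcile Subject Eligibility with the contraindication that Possible Risks already states, and make the Inclusion and Exclusion Criteria case report form agree if it has the same gap. How the reconciled text is worded is for the sponsor and the investigator; no new clinical rule is proposed here.

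In the same amendment, reconcile the eligibility row of the Schedule of Events with the Baseline (treatment) Visit section, so that both say when eligibility is assessed.

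The cost is about one line of criteria, one table entry and a short amendment. Almost no eligible patients should be lost, on the assumption above that few are affected. The sample size and the analysis do not change.

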By definition, HC responds to treatment with indomethacin, a nonsteroidal anti-inflammatory drug (NSAID) that has a structural similarity to serotonin and also inhibits nitric oxide-induced vasodilation^{4,5}. As with other indomethacin-responsive headache disorders, the mechanism by which it treats HC is not clear but there is some speculation that indomethacin may inhibit trigeminal nociceptive transmission and trigeminoautonomic activation^{6,7}. While patients with HC tend to respond within a matter of days to indomethacin, the literature reveals that most patients will relapse when it is discontinued and therefore will need to remain on it as a chronic treatment⁸. This can be problematic, as tolerability and risks of adverse effects with continued use remains a significant concern⁹. As an NSAID, the most common issue with indomethacin involves gastrointestinal complications, from indigestion and worsening acid reflux to gastric ulceration and hemorrhage. Patients may also experience renal insufficiency, and the drug can have an impact on blood pressure and platelet functioning among other things⁴. These risks are likely greater in patients with other co-morbid medical problems or on other

medications, or in the elderly who may have baseline renal and cardiac issues. There is a real need to find new treatment options for HC.

As there is significant overlap between HC and migraine, we anticipate that patients with HC will respond to treatment with erenumab.

Specific Aims:

1. Evaluate the response of hemicrania continua to treatment with erenumab
2. Evaluate the safety and tolerability of erenumab in patients with hemicrania continua

Methods:

Study Design: This is a prospective, open-label, study of patients with hemicrania continua treated with a single dose of erenumab 140 mg SQ.

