Erenumab will be stored refrigerated at 2°C to 8°C (36°F to 46°F) until time of use. Once removed from the refrigerator, it will be kept at room temperature and used within 7 days. Prior to administration, erenumab will sit at room temperature for at least 30 minutes, protected from direct sunlight.

Daily Headache Diary

A daily headache diary will be completed for the next 4 weeks to allow for assessment of changes in headache frequency and intensity. Headache diary data will be analyzed to classify patients as “responders” (50% or greater reduction in headache frequency at week 4 post erenumab treatment compared to frequency during the screening phase) or “non-responders” (less than 50% reduction in headache frequency at week 4 post erenumab treatment compared to the frequency during the screening phase). Since patient outcomes will be measured at 4 weeks (opposed to 12 weeks like it is done in the majority of clinical trials), depending upon patient outcomes other definitions of “response” and “non-response” could be used.

Acute Headache Therapy: Patients will be allowed to use acute headache treatments including NSAIDs during the study if needed. The use of these treatments will be recorded.

Table: Schedule of Events

	Screening Phase (7 days) (Day -7)	Baseline Visit (Day 0)	Weekly, weeks 1-4 (Day 0 to Day 28)	Follow-up Visit, week 4 (Day 28)	Safety follow-up visit, week 8 (Day 56)
Visit Window (days)	-2	+/- 0	n/a	+/- 3	+/- 3
Eligibility: I/E criteria	X				
Vital signs	X	X		X	X
Demographics, PMH	X				
Urine pregnancy test	X	X			
Headache characteristics	X			X	X
Concomitant medications / treatments	X			X	X
BDI		X		X	
STAI		X		X	
MIDAS		X		X	
PGIC				X	
Adverse events			X	X	X
Headache diary, daily	X		X		
Treatment: Erenumab injection		X			

Sample Size

A sample size of 20 will have 80% power to detect a decrease of frequency of headache days (in 28-day period) of 2 or more from baseline, assuming a standard deviation of 3, using a paired t-test with a 0.05

two-sided significance level. It is anticipated that up to 25 patients will be enrolled in the study in order to obtain 20 evaluable patients for the primary outcome.

Subject Recruitment and Screening

Subjects will be recruited from the Mayo Clinic Arizona Headache and Neurology clinics, from the clinical practices of colleagues practicing in the Phoenix region, and via posting of IRB-approved recruitment materials.

Subject Compensation

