Acute medication use (# days over weeks 4): Acute medication use at the end of week 4 will be compared as separate time points to baseline. Medication usage will be analyzed similar to specific aim #1 as above.

Remission rate (proportion of patients free of headache weeks 4): The proportion of patients who do not have any occurrence of headache at the end of week 4 will be divided by the total number of evaluable patients in the study. A point estimate and confidence interval will be computed for these endpoints, headache freedom at week 4.

Patient-reported Outcomes: Patients will complete the BDI, STAI, MIDAS, 4-week Follow-up Headache Characteristics and the PGIC. Patient reported outcomes (BDI, STAI, MIDAS) will be scored using published scoring algorithms and described at each time point using the mean, 95% confidence interval, median, and range. Changes from baseline will also be described using the mean, 95% confidence interval, median and range, and assessed using paired t-tests or Wilcoxon signed-rank tests as appropriate. Graphical procedures will include plots of average values over time. The PGIC will be described to assess patient perception of improvement.

Adverse Events Analysis: The proportion of subjects experiencing adverse events, the nature of the adverse events, as well as severity and relationship of the adverse events to the study will be reported using descriptive statistics. The proportion of subjects with adverse events that led to withdrawal from the study will also be reported. All subjects who received at least one dose of erenumab will be included in the safety analysis. The maximum grade for each type of adverse event will be summarized as the number of patients experiencing the event divided by the total number of evaluable patients. Frequency tables will be constructed. Additionally, the relationship of the adverse event(s) to the study treatment will be taken into consideration.

Results Reporting on ClinicalTrials.gov: At study activation, this study will have been registered within the “ClinicalTrials.gov” website. The Primary and Secondary Endpoints (ie, “Outcome Measures”) along with other required information for this study will be reported on ClinicalTrials.gov.

Protocol Approval and Maintenance by IRB

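### No vital signs are scheduled between Day 0 and Day 28 (±3) and none are analysed, so early hypertension is captured only through weekly adverse-event reports

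*Combined protocol and SAP*

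**What the plan says.** Under Possible Risks, the protocol lists new or worsening hypertension, known from post-marketing use, and adds: "Hypertension may occur at any time during treatment but was most frequently reported within seven days of dose administration". Study Design describes patients "treated with a single dose of erenumab 140 mg SQ", so each patient has one post-dose period.

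The Schedule of Events marks vital signs at four visits: screening, baseline, Week 4 and Week 8. The cell is blank in the column headed "Weekly, weeks 1-4 (Day 0 to Day 28". That column carries only adverse events and the headache diary. The Week 4 and Week 8 visits each have a window of ±3 days. The Day 0 reading appears with the eligibility checks, ahead of the treatment section: "Patients who still meet eligibility criteria will have measurement of vital signs".

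The Case Report Forms list includes a vital signs form. Statistical Methods & Analysis and Analysis Plans do not mention those data. The only safety analysis is of adverse events, where their nature, "as well as severity and relationship of the adverse events to the study will be reported using descriptive statistics".

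On indomethacin, the background states that "the drug can have an impact on blood pressure and platelet functioning". The Screening Phase section stops it at the screening visit for patients taking it to prevent hemicrania continua. Acute Headache Therapy allows NSAIDs during the study and says their use is recorded.

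**The concern.** The protocol names a risk and says when it has most often been reported, but schedules no measurement in that period. It also collects vital signs at two post-dose visits and plans no summary of them. Safety and tolerability is Specific Aim 2, so this bears on a stated objective.

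What is at stake is how a finding of little or no hypertension would be read. It could mean that pressures did not rise, that a rise came and went unmeasured, or that a rise was measured but nobody entered it as an adverse event. The planned output cannot separate these.

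The choice of baseline adds to this. For patients who enter on indomethacin, the screening reading may be taken on a drug that the protocol says can affect blood pressure, while the Day 0 reading comes a week after it is stopped. The plan does not say which reading a later one should be compared with.

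**Working it through.** The plan gives no calculated figure on this point, and its sample-size calculation does not enter. The check is day arithmetic on the Schedule of Events, followed by a comparison of sections.

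**Timing of post-dose readings**

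- Inputs: dose on Day 0; Week 4 visit on Day 28 ±3; Week 8 visit on Day 56 ±3; period named under Possible Risks, the first 7 days.
- First post-dose reading: 28 − 3 = Day 25 to 28 + 3 = Day 31.
- Gap after the seven-day period: 25 − 7 = 18 days to 31 − 7 = 24 days.
- Second post-dose reading: 56 − 3 = Day 53 to 56 + 3 = Day 59.
- Scheduled post-dose vital signs in days 1-7: 0 of 2.
- Weekly adverse-event collections covering the first week: 1.

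**Data without a planned analysis**

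- 20 evaluable patients × 4 visits = 80 sets of vital signs.
- Of these, 20 × 2 = 40 are post-dose. If all of the up to 25 enrolled patients were treated, 25 × 2 = 50.
- Planned summaries of these data: none.

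**What each route can detect**

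- *Week 1 rise that causes symptoms, is found on a home reading or is diagnosed elsewhere:* captured if the patient reports it at a weekly collection. The adverse-event sections require an onset date and count worsening of an existing condition.
- *Week 1 rise that nobody reports and that resolves before the Week 4 visit (Day 25 at the earliest):* never measured.
- *Rise still present at Week 4 or Week 8:* measured, but it reaches the results only if the investigator judges it an adverse event. No section says when a measured change becomes one, and no change from baseline is tabulated.

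**Baseline**

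Indomethacin is stopped at the screening visit and Day 0 is one week later. For those patients, change from screening would mix any effect of erenumab with the effect of stopping indomethacin. Change from Day 0 removes most of that problem. It does not remove all of it, because acute NSAIDs are allowed throughout.

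**The case against.** The strongest reply is that the protocol does watch the first week. Adverse events are collected weekly from Day 0 to Day 28, every event seen by the investigator or mentioned by the patient is to be recorded through Week 8, and onset dates are required. A worrying reading at Week 4 or Week 8 can itself be entered as an adverse event and then analysed. This stands. A reader might infer that the trial cannot see hypertension at all, or that any rise goes unnoticed until Week 4; the documents support neither.

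The risk statement should not be over-read either. It describes when post-marketing cases were reported, gives no rate, and says hypertension may occur at any time. It promises no early monitoring, so it and the schedule do not strictly contradict each other. This also stands, but it favours analysing the later readings: if the risk can arise at any time, Day 28 and Day 56 are informative, and neither is summarised.

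A third reply is that about 20 patients, one dose and no control arm cannot attribute a pressure change to erenumab. That is correct. Even no events in 20 patients would leave a one-sided 95% upper bound of 1 − 0.05^(1/20) = 13.9% (11.3% with 25). The adverse-event summary has the same limits and is planned anyway; a description of data already collected needs no power.

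**Conclusion.** The point holds as a gap in measurement and a gap in analysis. No vital signs are scheduled from the dose until Day 25 at the earliest (Day 31 at the latest), and the roughly 40 post-dose sets have no planned summary. Two things are lost: an unreported rise that resolves before the Week 4 visit, and any measured change that is not judged an adverse event. The documents give no rate for either, so the number of patients affected cannot be estimated.

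The analysis gap is the firmer part, because it can be closed with existing data. The effect is on what the trial can say under Specific Aim 2. The primary endpoint, power and sample size are untouched.

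This rests on three assumptions:

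- Vital signs include blood pressure, which the protocol does not spell out.
- The Day 0 reading precedes the injection, as the order of the text implies without stating it.
- One dose is given, as Study Design says. Protection Against Risks refers to two treatments, but no second dosing visit appears in the schedule.

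**What to change.** 1. In Analysis Plans, next to Adverse Events Analysis, add a descriptive summary of systolic and diastolic blood pressure at each visit, with change from Day 0 at Week 4 and Week 8. Name Day 0, not screening, as the baseline for this summary, and confirm that it is read before the injection. Show recorded NSAID use alongside. The cost is one table from data already collected. The remaining weakness is that Day 0 may still reflect acute NSAID use, which is why that use should be shown.

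2. Reconcile the vital-sign row of the Schedule of Events with the seven-day period under Possible Risks. Whether and when to add a reading, and what rise counts as an adverse event, are for the sponsor to decide. If the schedule stays as it is, a sentence giving the reason would be enough.

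3. Unless a first-week reading is added, state in the safety report that no blood pressure was scheduled in the first week after dosing and that hypertension in that period was captured through adverse-event reports only. This costs one sentence.
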